6.3 Duration of Therapy

Duration of therapy is dependent on donor and recipient antibody status.

Adult subjects will be treated with their assigned study drug (ValA or ValG) for **three months**, unless the donor is antibody positive and the recipient is antibody negative (D+R-) to CMV/EBV, then patient will get six months of prophylaxis.

Pediatric transplant recipients will be treated for **twelve months except** if both the donor and the recipient are antibody negative (**D- R-**) for both CMV and EBV, subjects will be treated for **three months**.

Patients that are randomized to ValA that develop CMV disease or CMV viremia X2 may discontinue ValA and begin standard of care treatment with ValG. At that time they will continue research related follow up but ValA use is up to the discretion of the treating physician. At that time all protocol directed safety follow up will be discontinued; however, outcomes will be followed until month 12.

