Subjects will be assessed weekly then monthly for medication compliance, as well as assessing adverse events. Subjects will be assessed at their routine clinic visits, or via email/telephone. Subjects will be followed for a total of 12-13 months, or for an additional 30 days after stop of the drug for adverse events.

Blood samples will be collected by using left-over standard of care samples for immunosuppression drug analysis. From these samples, qualitative PCR assay (qPCR) will assess CMV and EBV for up to six months post study drug cessation. Complete blood count and metabolic panels will be collected clinically, and results recorded for this study. CMV and EBV IgG and IgM levels will be measured bi-annually until seroconversion. In the cases where blood is not drawn for clinical purposes at least once a month, 10-15ml of the subject's blood may be collected for this testing for research purposes. Surveillance kidney transplant biopsies are obtained at the time of transplant, 3 months post-transplant, 12 months post-transplant, and as clinically indicated. For the duration of subject study participation, kidney tissue (two to three cores) from any biopsy will be shared with the research team.

Subjects will be followed-up regularly by the research team during the first year post transplant. During these follow-up assessments, the research team will assess drug adherence as well as evaluate side effects. If subjects are seen during a standard of care visit, laboratory values and a review of medical records will also be performed to assess any potential adverse events.

4 Subject Selection and Withdrawal

4.1 *Inclusion Criteria*

- Adult or pediatric kidney transplant recipients
 - Adult cases are defined as patients transplanted and cared for at the University of Minnesota Medical Center, East Bank campus.
 - Pediatric cases are defined as patients transplanted and cared for at the University of Minnesota Masonic Children's Hospital.
- Consent to participate in the study.

4.2 *Exclusion Criteria*

- Documented allergy to valA or valG

- Recipients that are unable to independently understand the consent form.
- Pregnant

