4.3.2 Data Collection and Follow-up for Withdrawn Subjects

Subjects will be followed for 12-18 months post-transplant procedure. Please refer to Table 1 for data points and frequency.

5 Study Procedures

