5.4 Schedule of Events

All assessments will be completed during routine clinical visits when feasible. If the participant does not have a scheduled clinic visit, the participant or parent/guardian can choose to receive an email or phone call follow-up of drug adherence and adverse events. Assessments will continue until at least 30 days after last dose of anti-viral.

Visit Schedule	Pre-KTx	KTx	Weekly During Month 1	Monthly through End of Study Period
CBC and BMP ¹ (routine clinical lab)	X		X	X
CMV PCR, EBV PCR ² ([name] research lab)	X		X	X
CMV IgG, EBV IgG & IgM ² ([name] research lab)	X			X ³
Acyclovir levels				X ⁴
Kidney bx tissue ⁵		X		X ³
Medication compliance			X	X ⁶
Adverse Events assessment			X	X ⁶

1 CBCs and BMP are performed routinely in post-transplant patients. If these are not done clinically, we will collect and perform for research safety monitoring

2 PCRs will be run using leftover blood collected clinically. If no leftover blood is available, we will collect a research specimen.

- 3 Month 6 only
- 4. Month 1 only if randomized to valA
- 5. Kidney biopsies are performed routinely during the first year post-transplant. Paraffin-embedded scrolls will be requested from leftover tissue.
- 6. Completed monthly until 1 month after cessation of the treatment

6 Study Drug

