- Risks related to steroids
- Hypertension
- Cardiovascular disease
- Diabetes
- Malignancy

Adverse Event Reporting Period

The study period during which adverse events must be reported is normally defined as the period from the initiation of any study procedures to the end of the study treatment follow-up. For this study, the study treatment follow-up is defined as 30 days following the last administration of study treatment.

Preexisting Condition

A preexisting condition is one that is present at the start of the study. A preexisting condition will be recorded as an adverse event if the frequency, intensity, or the character of the condition worsens during the study period.

General Physical Examination Findings

At screening, any clinically significant abnormality will be recorded as a preexisting condition. At the end of the study, any new clinically significant findings/abnormalities that meet the definition of an adverse event will also be recorded and documented as an adverse event.

Post-study Adverse Event

All unresolved adverse events will be followed by the investigator until the events are resolved, the subject is lost to follow-up, or the adverse event is otherwise explained. At the last scheduled visit, the investigator will instruct each subject to report any subsequent event(s) that the subject, or the subject's personal physician, believes might reasonably be related to participation in this study.

Abnormal Laboratory Values

A clinical laboratory abnormality should be documented as an adverse event if any one of the following conditions is met:

- The laboratory abnormality is not otherwise refuted by a repeat test to confirm the abnormality
- The abnormality suggests a disease and/or organ toxicity
- The abnormality is of a degree that requires active management; e.g. change of dose, discontinuation of the drug, more frequent follow-up assessments, further diagnostic investigation, etc.

Hospitalization, Prolonged Hospitalization or Surgery

Any adverse event that results in hospitalization or prolonged hospitalization will be documented and reported as a serious adverse event unless specifically instructed otherwise in this protocol. Any condition responsible for surgery should be documented as an adverse event if the condition meets the criteria for an adverse event.

Neither the condition, hospitalization, prolonged hospitalization, nor surgery are reported as an adverse event in the following circumstances:

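### Section 6.3 ends safety follow-up for valA patients at CMV failure or switch, contradicting the 30-day adverse event window stated elsewhere, with no matching rule for valG

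*Combined protocol and SAP*

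**What the plan says.** Section 6.3 sets a rule for one arm: "Patients that are randomized to ValA that develop CMV disease or CMV viremia X2 may discontinue ValA and begin standard of care treatment with ValG". It adds "At that time they will continue research related follow up", leaves further valA use to the treating physician, and closes with "At that time all protocol directed safety follow up will be discontinued; however, outcomes will be followed until month 12".

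Four other places govern follow-up after a subject stops drug:

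- Section 3 follows subjects for 12-13 months "or for an additional 30 days after stop of the drug for adverse events".
- Section 5.4 says "Assessments will continue until at least 30 days after last dose of anti-viral". Footnote 6, attached to compliance and AE assessment, reads "Completed monthly until 1 month after cessation of the treatment".
- Section 8, under the AE reporting period, says "the study treatment follow-up is defined as 30 days following the last administration of study treatment".
- Section 4.3.2, on withdrawn subjects, says "Subjects will be followed for 12-18 months post-transplant procedure. Please refer to Table 1 for data points and frequency".

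None of these makes an exception for a valA patient who moves to valG. Section 4.3.1 lists CMV disease needing valG as a reason to come off drug, without limiting it to one arm and without ending safety follow-up.

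**The concern.** Staff cannot follow section 6.3 and the other sections together. After the switch, one rule requires no safety follow-up and the others require at least 30 days of it.

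The second problem is comparability. The cut-off applies to valA only, and what sets it off is CMV disease or repeated viremia, an efficacy event after randomisation. A valG patient with the same viremia stays under AE assessment until 30 days after the last dose. Section 6.9 confirms that the trial is unblinded. How actively AEs are sought would therefore depend on both arm and outcome, so the missing safety data would not be missing at random.

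The between-arm safety comparison and the DSMB's safety review (section 8.4.1) are exposed, and primary endpoint 2 (side effects requiring dose reduction or cessation) may be. There is also a participant-safety aspect. Switchers start a drug whose common effects in section 6.6 include hematologic toxicity, and a patient whose physician keeps them on valA could be taking study drug with no protocol safety follow-up.

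**Working it through.** The plan gives no figure for this point, so the check is mainly a comparison of texts, followed by arithmetic for scale.

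**1. AE window after stopping valA**

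| Source | Window after the last valA dose |
|---|---|
| Section 6.3 | 0 days of protocol safety follow-up |
| Section 3 | 30 days |
| Section 5.4, text | at least 30 days after the last antiviral dose |
| Section 5.4, footnote 6 | 1 month |
| Section 8 | 30 days |
| Section 4.3.2 | scheduled data points, 12-18 months after transplant |

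If antiviral in section 5.4 includes the valG started at the switch, the required window runs to 30 days after that valG ends, and the gap widens.

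**2. Start of the cut-off.** Section 6.3 does not make clear whether its cut-off dates from the CMV event or from the switch. On the first reading, a patient who stays on valA is also affected.

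**3. How much scheduled AE follow-up is at stake.** Length of prophylaxis is from section 6.3, plus 1 month from footnote 6:

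- Most adults: 3 + 1 = month 4.
- Adults with a positive donor and negative recipient: 6 + 1 = month 7.
- Most children: 12 + 1 = month 13.
- Children where donor and recipient are negative for both viruses: 3 + 1 = month 4.

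The loss runs from the trigger to these points, or to 30 days after post-switch valG if that counts.

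**4. Number of patients.** Inputs: 200 recipients (section 7.4), 1:1 allocation (section 3), and 80% of valA patients free of CMV viremia at 6 months (section 7.4).

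- valA patients: 200 / 2 = 100.
- Viremic by 6 months: 100 × (1 − 0.80) = 20. This is the ceiling, reached only if every viremic patient meets the trigger on valA and switches.
- If half do so: 20 × 0.5 = 10.

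The figure could be lower. The trigger needs disease or repeated viremia, the switch is optional, and an adult on 3 months of prophylaxis whose viremia appears between months 3 and 6 has no valA left to discontinue. The documents give no rate of repeated viremia on drug or of switching.

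**5. What is still captured.** PCR and outcomes continue to month 12. Section 8 follows unresolved AEs, and section 8.1 requires later SAEs that may be related to be recorded and reported. CBC and BMP are routine clinical tests. What is exposed is active collection of new non-serious AEs, together with the study's undertaking in section 5.4, footnote 1, to do CBC and BMP when the clinic does not.

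**6. Effect on primary endpoint 2.** The matching objective in section 2 compares reduction or cessation of valA with that of valG because of side effects. Once valA has stopped, no further valA reduction or cessation can occur unless the physician restarts it. The uncollected events are then new AEs soon after valA ends and side effects of the valG that follows. If post-switch events count in the randomised arm, the valA count can be too low. If they do not, endpoint 2 is largely untouched, but the general AE comparison is still affected. The plan does not say which applies.

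**The case against.** The strongest defence is that section 6.3 separates two activities: research and outcome follow-up continues, while study-drug safety monitoring ends because the patient is on standard care. Section 5.3 assigns monthly safety labs specifically to valA recipients, which could explain why the rule names only that arm. Part of this stands. Continuing research follow-up while stopping safety follow-up is not in itself a contradiction. But the sentence covers all safety follow-up, defines no narrower meaning, and cannot be squared with the windows in sections 3, 5.4 and 8.

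A reader might also infer three stronger things that the documents do not support:

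- *Switchers lose AE follow-up for the rest of the year.* For most adults, AE assessment would end near month 4 or 7 in either arm. Only children on twelve months of prophylaxis would normally have about a year of it.
- *The rule makes valA look safer.* That direction is possible, but it presumes that side effects of post-switch valG count against valA, which the plan does not settle. The shorter time at risk on valA comes from the switch itself, and continued AE collection would not restore it.
- *All late valA events are lost.* Unresolved AEs and possibly related later SAEs remain covered, so the exposure is mainly new non-serious events.

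**Conclusion.** The point holds as a conflict between sections with a one-arm consequence. Section 6.3 cannot be followed together with the AE windows in sections 3, 5.4 and 8 or the follow-up of withdrawn subjects in section 4.3.2. If it is followed as written, active AE collection can stop early in the valA arm alone, after an efficacy failure, in an unblinded trial. This can bias the between-arm safety comparison. Bias on primary endpoint 2 is possible but not shown.

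The size is uncertain: at most about 20 of 100 valA patients, about 10 if half meet the trigger on drug and switch, and possibly fewer. These numbers rest on the plan's 80% viremia-free figure and on assumed switching proportions. The textual conflict does not depend on them. The sponsor should correct it.

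**What to change.** Delete the section 6.3 sentence that stops safety follow-up, and reconcile that section with sections 3, 4.3.2, 5.4 and 8:

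- Apply one identical rule for AE and safety-lab follow-up to both arms. The window already in the protocol serves: at least 30 days after the last antiviral dose, including valG taken after a switch. A month-12 AE window for switchers only should be avoided, because it would follow most adult switchers longer than other subjects and create a new imbalance.
- State that the outcomes followed to month 12 are the viremia endpoints.
- Report AEs after the switch by randomised arm, identifying the drug being taken at onset, and state whether such events count toward primary endpoint 2.

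These changes concern data collection and reporting, not how patients are treated. The cost is a wording amendment and slightly more AE data for switchers, mostly at contacts already planned for outcome follow-up.

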6.4 Method for Assigning Subjects to Treatment Groups

Subjects will be randomized by the IDS pharmacy in 1:1 fashion using computer allocation to receive either ValA or ValG, and will notify the study team of the randomization assignment

6.5 Preparation and Administration of Study Drug

After randomization, the treating investigator will order the treatment following this protocol dosing schema (see Tables 2 and 3). Commercial supply of ValA and ValG will be dispensed to the subjects.

6.6 Known Adverse Effects

As extracted from the package inserts for the study drugs, these are the known adverse effects for this protocol.

	Val G	Val A
COMMON Side Effects	headache nausea abdominal pain hematologic toxicity diarrhea fever tremor	headache nausea abdominal pain

	graft rejection vomiting hypertension upper respiratory infection urinary tract infection insomnia	
RARE adverse reactions	acute renal failure allergic reaction bleeding complications nervous system effects: agitation, hallucinations, confusion, delirium, seizures, swelling of the brain general pain, fatigue, weakness, edema abnormal lab results that might indicate abnormal organ function skin rash cough shortness of breath	acute renal failure allergic reaction bleeding complications nervous system effects: agitation, hallucinations, confusion, delirium, seizures, swelling of the brain

6.7 **Subject Compliance Monitoring**

Subjects will be asked to adhere to their prescribed treatment and dosage. Medication adherence will be assessed by the study team during routine visits, by reviewing the medical record, and by communication with the subject or guardian (table in section 5.4).

6.8 **Prior and Concomitant Therapy**

All prior and concomitant therapies will be documented and allowed as per standard of care procedures. Provided there are no direct interactions with the randomized medication, all medications will be prescribed as standard of care. Management of all viral disease is as per physician and will not be protocolled by research procedures.

6.9 **Blinding of Study Drug**

Not applicable.

7 Statistical Plan

7.1 Primary Study Endpoints

The primary study endpoints are as follows:

1. Incidence and duration of CMV and EBV viremia and magnitude of viremia as measured by area under the viral load-time curve of recipients who become viremic with CMV and/or EBV in the first year post-Ktx.
2. Incidence of subjects developing drug related side effects requiring dose reduction or cessation.
3. Presence of EBV and or CMV in renal tissue (protocol biopsies).

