10.2	AUDITING AND INSPECTING.....	23
11	ETHICAL CONSIDERATIONS	23
11.1	INFORMED CONSENT	23
12	STUDY FINANCES.....	23
12.1	FUNDING SOURCE.....	23
12.2	CONFLICT OF INTEREST.....	24
13	PUBLICATION PLAN	24
14	REFERENCES	25

List of Abbreviations

AE	Adverse Event
BID	twice daily
BMP	basic metabolic panel
CBC	complete blood count
CFR	Code of Federal Regulations
CMV	cytomegalovirus
CRF	Case Report Form
DSMB	Data and Safety Monitoring Board
DSMP	Data and Safety Monitoring Plan
EBV	Epstein-Barr virus
FDA	Food and Drug Administration
GCP	Good Clinical Practice
HIPAA	Health Insurance Portability and Accountability Act of 1996
ICH	International Conference on Harmonization
IDS	Investigational Drug Services
IRB	Institutional Review Board
KTx	kidney transplant
PCR	Polymerase Chain Reaction
PHI	Protected Health Information
SAE	Serious Adverse Event
QD	once daily
QOD	every other day
valA	valAcyclovir
valG	valGanciclovir

Study Summary

Title	Valacyclovir versus Valganciclovir for Post-transplant Cytomegalovirus/Epstein-Barr Virus Prophylaxis: A Randomized Controlled Trial
Short Title	ValA vs ValG for Post-transplant CMV/EBV Prevention
Protocol Number	11.0
Phase	Pilot
Methodology	Randomized Control Trial
Study Duration	36 months
Study Center(s)	Single-Center
Objectives	To compare the effectiveness of valacyclovir (valA) to valganciclovir (valG) in the prevention of EBV and CMV viremia post-kidney transplant.
Number of Subjects	Total of 200
Diagnosis and Main Inclusion Criteria	Adult and pediatric kidney transplant recipients
Study Product, Dose, Route, Regimen	Valacyclovir Dose: 500-1500mg bid Oral
Duration of administration	3-12 months dependent on treatment assignment and donor and recipient viral serostatus in accordance with standard of care.
Reference therapy	Valganciclovir Oral
Statistical Methodology	Incidence of viremia will be compared using a two-sided Fisher exact test and viral load-time curve areas will be compared using a Mann-Whitney test. A p-value of ≤ 0.05 will be considered significant.

1 Introduction

Infections are now a leading cause of death and morbidity in kidney transplant recipients. Herpes viruses such as Epstein-Barr virus (EBV) and cytomegalovirus (CMV) are particularly troublesome.

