1.3 Previous Clinical Experience

The anti-EBV effect of valG has not been conclusively demonstrated or proven. On the other hand, data from infectious mononucleosis intervention trials document that two weeks of valA therapy resulted in a statistically significant reduction in oral EBV shedding, accompanied by a clinical benefit (1, 2), and valA is currently used for the therapy of severe cases of infectious mononucleosis in the community (1, 3).

Oral acyclovir has been shown to prevent CMV disease in post-KTx recipients (4-7) and valA in particular has been shown to reduce the incidence and delay the onset of CMV disease in both CMV seronegative patients ($P<0.001$) and CMV seropositive patients ($P=0.03$) (8). But since that trial did not include a comparison arm with the current standard of care which is valG and did not provide information on the anti-EBV effect of the valA, our study is critical in proving the effectiveness of valA for CMV and EBV prophylaxis.

ValG is associated with adverse events including diarrhea, fever, nausea, vomiting, tremor, leucopenia, neutropenia, anemia and thrombocytopenia in $\geq 20\%$ of patients based on their package insert which we have attached. ValG induced leucopenia often necessitates a reduction in immunosuppressive therapy, increasing the risk of allograft rejection. Fewer severe adverse events are related to valA, including rash (8%), abdominal pain (1% to 11%), nausea (5% to 15%), vomiting (less than 1% to 6%), headache (13% to 38%) and fatigue (8%). Very high doses of valA (8g/day) for post-KTx CMV prophylaxis was shown to have no severe or treatment-limiting side effects compared to placebo (8).

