1.4 Dose Rationale and Risk/Benefits

Prior research at the University of Minnesota has shown that valacyclovir 1g every 8 hours for a total daily dose of 3g is well tolerated and was associated with a reduction in EBV excretion (1) in patients with infectious mononucleosis. Subsequently a study done at the University of Minnesota to characterize the pharmacokinetics and explore the pharmacodynamics of acyclovir in plasma and oral washings of 8 subjects with EBV infectious mononucleosis receiving the same daily dose of valacyclovir (3g) as a twice daily dosing of 1500 mg twice daily demonstrated safety and showed that the quantity of EBV DNA in oral washings and blood, and the severity of illness, measured by a graded scale, decreased during treatment (9).

Therefore in order to increase the likelihood of compliance in our patients, we have decided to utilize 1.5g twice a day dosing of valacyclovir and since it was shown to be effective as therapy in the above study, we hypothesize that it will be adequate for anti-viral prophylaxis as intended in this study. The dose will of course be adjusted based on GFR and in pediatric patients based on their weight as detailed in package insert and below.

No major side effects are anticipated since even very high doses of valA (8g/day), for post-KTx CMV prophylaxis were shown to have no severe or treatment-limiting side effects compared to placebo (10).

2 Study Objectives

Primary Objectives:

To compare the effectiveness of valacyclovir (valA) compared valganciclovir (valG) in the prevention of EBV and CMV viremia post-KTx.

To compare the proportion of patients requiring dose reduction or cessation of valA compared to valG due to adverse drug side effects.

Secondary Objective:

To identify the presence and quantity of EBV and CMV in renal tissue biopsies from kidney transplant recipients.

3 Study Design

This is a single-center, prospective, randomized, pilot study of up to 200 kidney transplant recipients from the University of Minnesota Medical Center. Randomization of subjects will be in a 1:1 ratio to receive either ValA or standard of care regimen of ValG. Duration of therapy will be 3-13 months.

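### Section 7.1 lists three unranked primary endpoints (eight or nine comparisons) with one blanket p ≤ 0.05, so the chance of a false primary finding is above 5% on every count tried

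*Combined protocol and SAP*

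**What the plan says.** Section 7.1 gives three numbered primary endpoints:

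1. On viremia: "Incidence and duration of CMV and EBV viremia and magnitude of viremia as measured by area under the viral load-time curve", for CMV and EBV in the first year after transplant.
2. On side effects: "Incidence of subjects developing drug related side effects requiring dose reduction or cessation".
3. On virus in the graft: "Presence of EBV and or CMV in renal tissue (protocol biopsies").

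The Statistical Methodology row of the Study Summary names two tests: "Incidence of viremia will be compared using a two-sided Fisher exact test and viral load-time curve areas will be compared using a Mann-Whitney test". It then adds: "A p-value of ≤ 0.05 will be considered significant". No test is named for duration, side effects or tissue virus.

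Section 2 has two primary objectives, viremia and side-effect dose changes, with no ranking between them. Tissue virus appears there as the secondary objective: "To identify the presence and quantity of EBV and CMV in renal tissue biopsies from kidney transplant recipients".

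Section 7.4 sizes CMV only: 80% viremia-free at 6 months, a 10-point non-inferiority margin, 80% power and alpha 0.05. It says no power calculation is possible for EBV. It does not name CMV as the single primary comparison.

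**The concern.** When several comparisons share primary status and each is read at 0.05, the chance that at least one is significant by luck exceeds 0.05 unless the plan ranks them, splits alpha or requires all to succeed. This plan does none of these.

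The stake is the trial's main conclusion. A mixed outcome is plausible, for instance CMV inconclusive with fewer dose changes on valA, or CMV worse and EBV better. As section 7 stands, either could be presented as a positive primary result. The treatment is open-label (section 6.9), which makes it more useful to fix the reading of the results in advance.

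**Working it through.** **Count of comparisons (section 7.1).** Incidence, duration and area under the curve for two viruses: 3 × 2 = 6. Side effects: 1. Tissue virus: 2 (CMV and EBV), or 1 if the endpoint means either virus. Total 9, or 8. Comparisons with a named test (incidence and area, two viruses): 4.

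**The plan's own figure.** The document states no overall error rate. Its only design figure is the 54 recipients in 7.4. With 80% in both arms and a 10-point margin, n per arm = (z_α + z_β)² × 2 × 0.8 × 0.2 / 0.10². At one-sided 0.05 this is 6.183 × 32 = 197.8, so 198 per arm. At one-sided 0.025 it is 7.849 × 32 = 251.2, so 252 per arm. The 54 does not reproduce. That is a separate problem; it matters here only for the cost of the possible fixes.

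**Independent tests.** Chance of at least one false positive = 1 − 0.95^k:

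| k | Reading | Result |
|---|---|---|
| 9 | all comparisons | 37.0% |
| 8 | tissue as one composite | 33.7% |
| 4 | named tests only | 18.5% |
| 3 | the numbered endpoints, one test each | 14.3% |

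**Correlated tests.** Nine equally correlated two-sided tests at 0.05, simulated as multivariate normal: 26.9% at r = 0.5, 20.2% at r = 0.7, 12.3% at r = 0.9.

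**Trial-level simulation under no difference.** There were 100 subjects per arm and 4,000 trials per scenario. Fisher's test was used for proportions; Mann-Whitney was used for area and duration, among viremic subjects only.

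- From the document: CMV rate 17% (section 1) with EBV 20% (adult rate, section 1).
- Second scenario: EBV 50% (pediatric rate, section 1) with an assumed CMV rate of 20%.
- Assumed: side-effect rate 20%; tissue positive in 40% of viremic and 5% of other subjects; tissue available for everyone; CMV and EBV viremia independent; correlation between duration and area 0.49 or 0.90.

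| Family | Any p ≤ 0.05, range over four scenarios |
|---|---|
| All nine | 25.8% to 30.3% |
| Four with named tests | 14.4% to 15.8% |
| CMV incidence, EBV incidence, side effects | 9.2% to 10.0% |

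The Monte Carlo standard error is at most about 0.7 points. The results fall below the independence figures because Fisher's test is conservative at these sizes (about 3–4% per test) and because some endpoints are correlated.

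**The case against.** **This is a pilot.** The Study Summary and section 3 say so, which softens the consequences. But 7.4 sets a margin, power and alpha for non-inferiority, and section 1.3 says "our study is critical in proving the effectiveness of valA for CMV and EBV prophylaxis". That sentence is background prose and should not carry much weight; the design parameters in 7.4 should. The label supplies no decision rule.

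**Not all nine are clearly tested.** This stands. A reader might infer that the plan tests nine comparisons at 0.05. Tests are named for four only; for the other five, testing is inferred from the blanket sentence, and section 2 words the tissue objective descriptively. The four alone still give 14–16%.

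**37% is too high.** This also stands. It needs independence, which is not credible for measures of the same virus or for viremia and tissue virus.

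**The error rate is for the wrong hypothesis.** Partly right. Section 7.4 frames CMV as non-inferiority, while the Study Summary names a two-sided difference test. The figures above describe difference tests and say nothing about the error of a non-inferiority conclusion.

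**The intended reading is joint.** Section 1.1 makes the benefit of valA depend on equal CMV efficacy together with some EBV efficacy. Under that reading, CMV worse with EBV better is not a success, so it would be too strong to say that the document gives no hint. It is rationale, however, and section 7 does not turn it into a rule.

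**Conclusion.** The point holds. On every count tried, from all nine comparisons down to three, the chance of at least one false primary finding is above 5%: about 26–30% for nine, 14–16% for four and 9–10% for three. This assumes difference tests at 0.05 and that any single significant result counts as a primary finding; under an all-must-succeed rule there would be no inflation, but none is stated. The simulated figures also depend on the assumed rates listed above.

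The endpoint list has two internal conflicts. Tissue virus is primary in 7.1 and secondary in section 2. CMV is sized at 6 months in 7.4 but measured over the first year in 7.1. A reader might infer that 7.4 sizes the first-year CMV comparison; it does not.

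**What to change.** In section 7:

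- Restrict the primary family to three comparisons that match the section 2 primary objectives: CMV viremia incidence, side effects leading to dose reduction or cessation, and EBV viremia incidence.
- Judge CMV by a confidence interval against the 10-point margin, at one time point reconciled between 7.1 and 7.4, and not by Fisher's difference test.
- Apply Holm at an overall 0.05: the smallest p-value against 0.05/3 = 0.0167, the next against 0.025, the last against 0.05, with the CMV interval set at the matching level.
- Move tissue virus to secondary, as in section 2. Report duration, area under the curve and tissue virus with 95% confidence intervals and no significance claim.

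**Cost.** Plan wording, with no added patients. Duration, area and tissue virus lose primary status, and the first Holm step is stricter. For CMV with 100 per arm and 80% viremia-free in both arms, SE = √(2 × 0.16/100) = 0.0566 and 0.10/0.0566 = 1.77. If CMV is tested at the first step, power is Φ(1.77 − 2.39) = about 27% at one-sided 0.0083 (half of 0.0167), or Φ(1.77 − 2.13) = about 36% at one-sided 0.0167. Section 7.4 does not say which sidedness it uses.

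**Alternative.** A fixed sequence that starts with CMV non-inferiority keeps 0.05 at each step, but its cost must be stated. Power at the gate is Φ(1.77 − 1.96) = about 42% at one-sided 0.025, or Φ(1.77 − 1.645) = about 55% at one-sided 0.05. So even if valA is truly equal, side effects and EBV would go formally untested in roughly half of such trials. Holm avoids making them wait on CMV.
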